1 LIST OF ABBREVIATIONS AND DEFINITIONS

- AE adverse event
- ALT alanine transaminase
- BUN blood urea nitrogen
- CL cutaneous leishmaniasis
- CRF case report form
- CTC Common Terminology Criteria
- DCL diffuse cutaneous leishmaniasis
- DNA deoxyribonucleic acid
- ENT ear-nose-throat
- ECG electrocardiogram
- FDA food and drug administration
- IND investigational drug application
- IRB institutional review board
- mITT Modified Intention-to-treat
- ML mucosal leishmaniasis
- MSS mucosal severity score
- PCR polymerase chain reaction
- PE physical examination
- PI Principal Investigator
- SAE serious adverse event

2 STUDY SCHEDULE

Time and Event Schedule									
Study Phase	Screening ^a		Treatment			Follow-up			
Study Day/Week/Month	Day -14 to -1	Day 1	Day 7 ± 3 days	Day 14± 3 days	Day 28	Week 6	Month 3	Month 7	Month 13 ^h
Informed Consent	X								
Demographics	X								
Medical History ^{b, c}	Х	Х	Х	Х	Х	Х	Х	Х	Х
Physical examination ^d	Х	Х			Х	Х	Х	Х	Х
Leishmanial History and Exam ^c	Х				Х	X	Х	X	X
Hematology	Х								
Blood Chemistries	Xe			X ^f	X ^f	X ^g	X ^g	X ^g	X ^g
ECG	Х								
Pregnancy Test	Х	Х	Х	Х	Х		Х	Х	
Eligibility Checklist	Х								
AEs		Х	X	Х	Х	Х	Х	Х	Х
Treatment			D	aily					

^aScreening includes the 14-day period for conducting screening procedures prior to the first administration of investigation product on Day 1.

^bIncludes medication history

^cIf subject does not appear at the scheduled Week 6, Month 3, Month 7, or Month 13 visits, these data may be obtained from the subject by telephone, and will be noted as obtained in that manner.

^dIncludes vital signs

^eScreening laboratories

^fAlanine transaminase (ALT) and creatinine on Day 28 and also on nominal day 14

^gIf abnormal on previous examination

^hML subjects only

3 ABSTRACT

The purpose of this Treatment Protocol is to make miltefosine immediately available for mucocutaneous leishmaniasis subjects presenting in the United States. Submission of an application for New Drug Approval is in process. Enrollment in this protocol makes it possible for subjects and their physicians to utilize miltefosine prior to approval.

If entrance criteria are met, subjects with mucosal or cutaneous leishmaniasis will receive miltefosine at a targeted dose of 2.5 mg/kg/day for 28 days. During the 28-day treatment period, the subject will return to the treatment facility at least three times for evaluations and recording of any AEs. Blood samples for the evaluation of transaminase and creatinine levels will be drawn at the midpoint and at the end of therapy.

Subjects will return to the treatment facility to be examined clinically at Study Week 6 (i.e., 2 weeks after the end of therapy), Month 3 (2 months after therapy), and Month 7 (6 months after treatment) for mucosal leishmaniasis (ML) and cutaneous leishmaniasis (CL) subjects. ML subjects will also be evaluated at Month 13 (12 months after treatment).

OBJECTIVES

Primary: Record the efficacy of miltefosine, approximately 2.5 mg/kg/day for 28 days, in the treatment of mucocutaneous leishmaniasis presenting in the United States.

Secondary: Record the tolerance of miltefosine, approximately 2.5 mg/kg/day for 28 days, in the treatment of mucocutaneous leishmaniasis presenting in the United States.

STUDY DESIGN

Open-label, single group, multicenter study.

POPULATION

- 1. Male or female at least 18 years of age.
- 2. Weight at least 30 kg.
- 3. Provided informed consent
- 4. ML or CL already demonstrated in at least one lesion by at least one of the following methods:
 - a. positive culture of lesion material for promastigotes,
 - b. microscopic identification of amastigotes in stained lesion tissue, or
 - c. PCR of lesion material.
- 5. No antileishmanial therapy in the previous 4 weeks.
- 6. Subject capable of understanding and complying with the protocol.
- 7. If female and of child-bearing potential, a negative pregnancy test during screening and agree to use an acceptable method of birth control during the treatment phase and for 6 months after treatment.
- 8. If female, not breast feeding.
- 9. No clinically significant medical disorder. Specifically:
 - a. Platelet count $>100 \times 10^9/L$
 - b. Leukocyte count $>3 \times 10^9/L$

- c. Hemoglobin >10 g/dL
- d. ALT <2 times upper limit of normal range
- e. Bilirubin <1.5 times upper limit of normal range
- f. Serum creatinine <1.5 times upper limit of normal range
- g. Major surgery within last 2 weeks
- h. Any non-compensated or uncontrolled condition
- 10. No known Sjogren-Larssen syndrome

INVESTIGATIONAL PRODUCT

Drug name: Miltefosine (50 mg capsules).

Dosing regimen: Approximately 2.5 mg/kg/day (maximum: 150 mg per day) for 28 days. Dose: The daily dosage for subjects of body weight 30-45 kg is 100 mg miltefosine (2 capsules Impavido 50 mg). Subjects with a body weight higher than 45 kg receive 150 mg miltefosine daily (3 capsules Impavido 50 mg). The dose is administered orally, with meals.

STUDY PROCEDURES

Subjects with ML or CL from which Leishmania have already been identified are potentially eligible to be treated with miltefosine via this protocol. Treating Physicians with potentially eligible subjects will contact the protocol Principal Investigator (PI), and receive the case report forms (CRF) from the PI. The Treating Physician will complete the screening CRF pages for demographics, medical history, leishmaniasis history, clinical laboratory results that are available, and identification of Leishmania in the lesion, and send the completed CRF pages to the PI. If after PI review, the subject is potentially eligible for the protocol, the PI will send the protocol, the miltefosine package insert, the informed consent form, and a blank copy of FDA form 1572 to the Treating Physician. Although this protocol will have already been approved by a "central" Institutional Review Board (IRB), if there is an additional need to have the Treating Physician's local IRB approve the protocol, the Treating Physician will obtain the approval, and obtain informed consent from the subject. The rest of the laboratory tests must be accomplished so that all screening laboratory tests are completed prior to enrolling a potential subject. If in the physician's opinion the subject appears eligible for enrollment, the Treating Physician will send to the PI the local IRB signature page (if needed), protocol signature page, informed consent signed by both the subject and the Treating Physician, the rest of the completed CRF pages for screening, and the form 1572 completed with the Treating Physician's information plus the Treating Physician's curriculum vitae. After the PI's review of these forms, the investigational product will be sent from the drug repository to the Treating Physician for that subject's use.

Treatment will be daily for 28 consecutive days. During treatment at weeks 1, 2, and 4, the subject will return to the treatment facility to be assessed for adverse events and to receive additional supply of medication if needed. Compliance with drug administration will be assessed by subject interview and pill count. Blood for transaminase and creatinine values will be drawn at the midpoint and at the end of therapy.

Subjects will return to the treatment facility to be examined clinically at Study Week 6, Study Months 3 and 7 months for ML and CL subjects, and also at Study Month 13 for ML subjects.

SAMPLE SIZE AND STUDY DURATION:

10-20 subjects per year for 1-5 years.

OUTCOME PARAMETERS:

Efficacy: Clinical response of lesions Safety: AEs

ANALYSIS:

Efficacy: The percent of subjects who have clinical cure of all lesions will be calculated. Safety: The occurrence and severity of AEs will be described.

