4.2.2 Contraindications

- Hypersensitivity to the active substance or any of the excipients
- Pre-existing severe damage of liver or kidney function

- Sjögren-Larsson-Syndrome
- Pregnancy and women of childbearing potential who do not use reliable contraception during and up to 3-6 months after treatment

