4.2.7 Clinical and Non-clinical Pharmacology

4.2.7.1 Pharmacodynamic Properties

Miltefosine has a marked direct antileishmanial activity *in vitro* and in animal models. However, the relevance of specific values (ED50, ED90) to clinical efficacy is unknown. The specific mode of action of miltefosine in leishmaniasis is unknown. Among other possible mechanisms, miltefosine can inhibit the metabolism of phospholipids in cell membranes of parasites.

Nonclinical Pharmacokinetic Studies

Distribution studies in rats, using radioactively labeled miltefosine, showed highest uptake of radioactivity in kidney, liver and spleen. Slow elimination of radioactivity from tissues (half lives 8-16 days) is partially explained by metabolism of miltefosine and incorporation of the labeled choline fragment into physiological lipids.

No oxidative metabolism by 15 different cytochrome P450 isozymes was observed *in vitro*. No CYP3A induction by miltefosine was found *in vivo*, in rats. Thus, no interaction has to be expected between miltefosine and drugs, like contraceptive hormones, that are metabolized by CYP3A. A slow metabolic breakdown could be shown in human hepatocytes, resulting in the release of choline by phospholipase D like cleavage of the miltefosine molecule. The fatty alcohol containing fragment of miltefosine can enter the metabolism of fatty acids after being oxidized to palmitic acid. This oxidation is blocked in subjects with Sjögren-Larrson syndrome, which is caused by a genetic defect in fatty aldehyde dehydrogenase activity. Preclinical and clinical studies suggest that only a very minor part of the administered dose will be excreted as the unchanged drug substance. Instead, choline and choline-containing metabolites are the most likely excretion products.

Pharmacokinetic studies in subjects with cutaneous leishmaniasis (Dorlo et al., 2008)

Subjects were administered miltefosine at an average dosage of 1.8 mg/kg/day. Pharmacokinetic analysis in this CL subject population resulted in calculation of two half lives: a first half-life of 7.0 days and a terminal half-life of 31 days.

Nonclinical Toxicology

Toxicological studies with miltefosine have been performed in mice, rats, dogs and rabbits. Adverse reactions not observed in clinical studies, but seen in animals at exposure levels similar to clinical exposure levels and with possible relevance to clinical use are described in the section below.

Acute and Chronic Toxicity

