7.1.2 Inclusion Criteria

To be eligible for the study, the following must be answered "YES" or not applicable as appropriate for the study subject:

- 1. Is the subject a male or female at least 18 years of age?
- 2. Does the subject weight at least 30 kg?
- 3. Does the subject have a diagnosis of ML or CL in at least one lesion by at least one of the following methods:
 - a. positive culture of lesion material for promastigotes,
 - b. microscopic identification of amastigotes in stained lesion tissue, or
 - c. PCR of lesion material?
- 4. In the opinion of the investigator, is the subject capable of understanding and complying with the protocol?
- 5. If female and of child-bearing potential, did the subject have a negative pregnancy test during screening and agree to use an acceptable method of birth control during the treatment phase and for 6 months after treatment is completed?
- 6. Has the subject signed informed consent?

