7.1.3 Exclusion Criteria

To be eligible for the study, the following must be answered "NO" or not applicable as appropriate for the study subject:

- 1. Is the subject a female who is breast-feeding?
- 2. Does the subject have a clinically significant medical disorder?
 - a. Platelet count $<100 \times 10^9/L$
 - b. Leukocyte count $<3 \times 10^9/L$
 - c. Hemoglobin <10 g/dL

- d. ALT, >2 times upper limit of normal range
- e. Bilirubin >1.5 times upper limit of normal range
- f. Serum creatinine >1.5 times upper limit of normal range
- g. Major surgery within last 2 weeks
- h. Any non-compensated or uncontrolled condition
- 3. In the last 4 weeks up to the present, has the subject received other treatment for leishmaniasis, including any medication with pentavalent antimony; amphotericin B, paromomycin, or imidazoles?

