9.2 Screening Procedures

Subjects will have the following procedures performed during a two week period prior to the initiation of investigational product:

- 1. Consent form completed and signed.
- 2. Demographics form completed.
- 3. Medical history form completed and record medications used in the past 2 weeks.
- 4. Physical examination form completed including vital signs, height, and weight.
- 5. Leishmaniasis history and physical form completed.
 - a. Record history of leishmaniasis including;
 - (1) CL: estimated date that the lesion(s) first appeared, evolution of symptoms, treatments to date
 - (2) ML: estimated date that the symptoms first appeared, evolution of symptoms, treatments to date

- b. CL subject examination: For each cutaneous lesion, record the size of the lesion ulceration (length/width), characteristics of the lesion (ulcerated versus non-ulcerated), and anatomical location. Examination of nasal skin, nasal mucosa, palate, and pharynx must be performed by the Treating Physician.
- c. ML subject examination: Examination of mucosal membranes. Each of 5 possible sites (nasal skin, nasal mucosa, palate, pharynx, and larynx) will be evaluated for 4 possible signs of disease (erythema, edema, infiltration, and erosion) by an ear, nose, and throat (ENT) specialist.
- 6. Pregnancy test from completed for women of child-bearing potential.
- 7. Hematology form completed to include white blood cells (WBC), neutrophil count, hemoglobin, hematocrit, and platelet count.
- 8. Chemistry form completed including glucose, sodium, potassium, creatinine, ALT, and bilirubin in the serum.

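### Sjögren-Larsson syndrome bars entry in the abstract and is a listed contraindication, but the eligibility lists in Sections 7.1.2 and 7.1.3 leave it out

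*Combined protocol and SAP*

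**What the plan says.** Three places in the protocol name the syndrome, with varying spelling:

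- Section 3 (Abstract), Population, criterion 10: "No known Sjogren-Larssen syndrome".
- Section 4.2.2, Contraindications: "Sjögren-Larsson-Syndrome".
- Section 4.2.7.1, on the metabolism of the drug's fatty-alcohol fragment: "This oxidation is blocked in subjects with Sjögren-Larrson syndrome".

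Section 7 sets out eligibility as yes/no questions. Both lists open with "To be eligible for the study, the following must be answered", requiring yes for the six inclusion items in 7.1.2 and no for the three exclusion items in 7.1.3. Neither list names the syndrome. The nearest item is exclusion 2, "Does the subject have a clinically significant medical disorder", followed by sub-items a to h. The last of these is "Any non-compensated or uncontrolled condition".

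**The concern.** The sponsor's intent to exclude these subjects is explicit, but it does not reach the section written as the eligibility test. Section 15.3 makes each Treating Physician responsible for determining eligibility from the inclusion and exclusion criteria. It gives no section number, but Section 7 is the only section with those headings. A physician who works from Section 7 alone meets no named bar.

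At stake is a possible safety error at entry: a subject with a listed contraindication could satisfy every Section 7 question and receive 28 days of drug. Section 4.2.7.1 makes a metabolic statement only. It describes no clinical harm and does not present the blocked oxidation as the reason for the contraindication.

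**Working it through.** The plan gives no figure to reproduce, so the check compares the lists.

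**Step 1. Match each abstract criterion to Section 7.**

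| Abstract criterion | Section 7 counterpart |
|---|---|
| 1 Age | Inclusion 1 |
| 2 Weight | Inclusion 2 |
| 3 Consent | Inclusion 6 |
| 4 Confirmed diagnosis | Inclusion 3 |
| 5 No recent antileishmanial therapy | Exclusion 3 |
| 6 Able to understand and comply | Inclusion 4 |
| 7 Pregnancy test and contraception | Inclusion 5 |
| 8 Not breast-feeding | Exclusion 1 |
| 9 No significant medical disorder (a to h) | Exclusion 2 (a to h) |
| 10 Sjögren-Larsson syndrome | None |

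Nine of the ten abstract criteria are matched. All 6 + 3 = 9 Section 7 items are used once, so none is left over to stand for criterion 10.

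**Step 2. Count the mentions.** The syndrome is named three times outside Section 7 (abstract, 4.2.2, 4.2.7.1). It is named in 0 of the 9 Section 7 items and 0 of the 8 sub-items of exclusion 2.

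**Step 3. Rule out a text-extraction fault.** Both Section 7 lists are numbered without a break, Section 8 follows directly, and there is no sign of redaction at that point.

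**Step 4. Ask whether exclusion 2 already does the job.** Its lead question is broad enough to cover the syndrome if the physician judges it clinically significant. Sub-items a to f are laboratory limits, g is recent surgery, and h reaches only a condition that is not compensated or not controlled. A stable, known case meets none of a to h. Abstract criterion 9 has the same lead and the same eight topics, yet the sponsor still wrote criterion 10 separately. Where the sponsor wrote out both, it did not rely on the general item alone.

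**Step 5. Size.** Section 7.1.1 plans 10 to 20 subjects a year for 1 to 5 years: 10 × 1 = 10 at the least and 20 × 5 = 100 at the most. The documents give no frequency for the syndrome, so no expected count can be computed.

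**The case against.** The best counter-case is that the protocol as a whole is consistent. The abstract calls its list entrance criteria, Section 7 states no contrary rule, and a physician who reads everything finds one instruction. Exclusion 2 also drops the word in abstract criterion 9 that introduces the sub-items as specifics. Its list need not be exhaustive, and a disorder the protocol itself contraindicates can fairly be called clinically significant for this drug. Nor does Section 7 copy 4.2.2 item by item: hypersensitivity is a contraindication that appears in neither the abstract list nor Section 7.

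There are also several safeguards:

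- Section 9.2 requires a medical history: "Medical history form completed and record medications used in the past 2 weeks".
- The PI reviews the screening forms before sending the study papers: "If after PI review, the subject is potentially eligible for the protocol, the PI will send the protocol, the miltefosine package insert".
- The PI reviews the completed forms again before drug is shipped (Section 9.1).
- Eligibility is verified with the PI before consent (Section 14.2).
- A checklist is completed before the first dose (Section 9.3.1), although its items are not in the documents.

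Much of this stands. The fault is an omission and not two opposed rules, exclusion 2 is arguable either way, and the safeguards make harm unlikely. The hypersensitivity point weakens the argument from 4.2.2 taken alone. It does not touch the mismatch with the abstract, where the sponsor did choose to make the syndrome an entry criterion. A discretionary reading of a general item remains weaker than a named bar, and none of the safeguards puts the criterion into Section 7.

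**Conclusion.** The concern holds. One of ten abstract criteria, and a listed contraindication, is missing from the eligibility lists in Section 7. As written, those lists could admit a subject the sponsor means to exclude.

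The practical effect is small, and this is a low-priority correction. Affected subjects are assumed to be very few or none among the 10 to 100 planned. That is an assumption, because the documents give no frequency. No endpoint, analysis population or analysis changes.

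Confidence is high that the item is missing. Whether a subject would actually be enrolled depends on how exclusion 2 is read and on what the checklist contains. If the checklist was built from Section 7 it would carry the same gap, but that cannot be verified here.

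**What to change.** Add a fourth numbered exclusion to Section 7.1.3 asking whether the subject has known Sjögren-Larsson syndrome, and confirm that the eligibility checklist carries the same question.

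The cost is one line of text and a check of one form. The criterion concerns known disease, so the medical history can answer it and no test or visit is added. If the study has already started, the change is a routine amendment through the central IRB (Section 15.1), with local IRB review where a site requires it (Section 13.2).

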4 INTRODUCTION AND RATIONALE

4.1 Mucocutaneous Leishmaniasis (Murray et al., 2005)

4.1.1 Clinical Spectrum

Sandflies inoculate the skin with flagellated *Leishmania* promastigotes, which invade or are phagocytosed by local and immediately recruited host cells. Within phagolysosomes of resident macrophages, surviving promastigotes transform and replicate as amastigotes, which infect additional macrophages either locally or in distant tissues after dissemination.

Multiple Leishmania species produce CL, primarily L. major, L. tropica, and L. (L.) aethiopica (Old world cutaneous leishmaniasis); L. infantum and L. chagasi (Mediterranean and Caspian sea regions); and L. mexicana, L. (L.) amazonenesis, L. braziliensis, L. (V.) panamensis, L. (V.) peruviana, and L. (V.) guyanensis (New World CL).

A papule typically begins at the sandfly bite, enlarges to a nodule, and ulcerates over 1–3 months. Flat plaques or hyperkeratotic or wart-like lesions also develop in Old World disease. Subjects, including travelers and military personnel, first seek attention because of one to two, or sometimes several (up to dozens) non-healing skin lesions on nocturnally exposed skin. In Old World CL, most lesions are papules, nodules, or nodule-ulcers, whereas ulcerative lesions are most common in New World CL. Disseminated lesions and localised lymphadenopathy preceding skin ulcers occur in Brazil. *L. tropica* infection disseminates in that new papules can appear around a healed lesion (leishmaniasis recidivans).

Mucosal dissemination of New World species (*L. braziliensis, L. panamensis, L. guyanensis*) occurs in 1-10% of infections, developing 1-5 years after cutaneous leishmaniasis has healed, but sometimes coincident with active skin lesions; about 90% of subjects have a preceding cutaneous scar. ML typically begins with erythema and ulceration at the nares, proceeding to nasal septum perforation and destructive inflammatory lesions. The latter can obstruct the pharynx or larynx and produce remarkable disfigurement. Mucosal disease is occasionally reported outside of Latin America, and can be acquired by travelers.

4.1.2 Diagnosis

Diagnosis is routinely made microscopically by identification of amastigotes in biopsies, scrapings, or impression smears. Combination of microscopy and culture increases diagnostic sensitivity to more than 85%, and culture (or DNA analysis) allows species identification. Detection of parasite DNA in lesion material by polymerase chain reaction (PCR), although generally only performed in research settings, is usually most sensitive in the diagnosis of both cutaneous and mucosal leishmaniasis.

4.1.3 Treatment with Classical Agents

Cutaneous disease heals by re-epithelialization with scarring. Most Old World lesions self-cure within 2–4 months (*L. major*) or 6–15 months (*L. tropica*). In New World CL, self-healing after 3 months is rapid in *L. mexicana* (~75%), but slow in *L. braziliensis* (about 10%) and *L. panamensis* infections (about 35%).

CL is treated to accelerate cure, reduce scarring especially at cosmetic sites, and to attempt to prevent dissemination (eg, mucosal disease) or relapse. Treatment is especially likely to be given for persistent lesions (>6 months) or lesions that are located over joints, multiple (5–10 or more), or large (4–5 cm or more). Classic treatment with parenteral antimony would probably be successful in CL in all regions; however, up to 20 daily injections of this moderately toxic drug approximates the morbidity of self-healing disease itself.

ML can produce potentially life-threatening inflammatory disease and must be treated. The standard regimen, 28 days of parenteral antimony, induces cure in around 75% of cases of mild disease (nares only), but advanced disease responds less well. Amphotericin B can be used as rescue therapy.

